10. IRB/PROTECTION OF HUMAN SUBJECTS

Please describe the process for protection of human subjects, and IRB review and approval of the proposed program and evaluation plans. Name the specific IRB to which you expect to apply.

Solutions IRB, a private commercial Association for the Accreditation of Human Research Protection Programs Inc. (AAHRPP) fully accredited Institutional Review Board, will ensure that this study is approved before any research activities take place. MER has had 14 research studies approved by Solutions IRB over the past four years, has completed over 15 annual check-in reports, and has submitted timely amendments when changes to studies needed to take effect.

All submissions are completed online, so turnaround for a new study approval is between 24 to 72 hours, though the full approval process can take approximately one to two weeks depending on the number of questions and requested revisions that the IRB makes. In the IRB application submission, we will include descriptions of project staff, locations of study sites, the funding source, incentives, summary of activities, participant population, recruitment plans, risks and benefits, confidentiality of data, and the informed consent process along with all materials to be used in the study such as participant forms and surveys.

This project was submitted for IRB approval in early March 2021 and received official approval to begin enrollment and data collection in March 2021. Amendments to the original application were approved in April 2022 and will be submitted as necessary based on programmatic or evaluation changes.

11. DATA

11.1. DATABASES

For each database used to enter data, please describe the database into which data will be entered (i.e., nFORM and/or other databases), including both performance measure data you plan to use in your local evaluation and any additional local evaluation data. Describe the process for data entry (i.e., who will enter the data into the database).

Database Name	Data Entered	Process for Data Entry
nFORM	Performance measurement data, local evaluation data	Entered directly by participants, and by program staff
Qualtrics	Local evaluation data, participant outcomes (OLLE survey)	Entered directly by participants, and by MER evaluation staff

11.2. DATA REPORTING AND TRANSFER

For each database provided in the table above, please indicate the ability to export individual-level reports to an Excel or comma-delimited format and whether identifying information is available for linking to data from other sources.

Database Name	Ability to Export Individual Reports?	What identifying information is available to facilitate linking to other data sources?
nFORM	Yes using Data Export function	nFORM ID, name, date of birth
Qualtrics	Yes, Excel or comma-separated	nFORM ID, name, date of birth

* you may add rows by hitting the tab button, or right click and select insert row below

11.3. CURRENT SECURITY AND CONFIDENTIALITY STANDARDS

For each database provided in Section 11.1, please Indicate the ability to be able to encrypt data access during transit (for example, accessed through an HTTPS connection); be able to encrypt data at rest (that is, when not in transit), have in place a data backup and recovery plan; require all users to have logins and passwords to access the data they are authorized to view; and have current anti-virus software installed to detect and address malware, such as viruses and worms.

Database Name	Ability to encrypt data during transit?	Ability to encrypt at rest?	Data Backup and Recovery Plan?	Require all users to have logins and passwords?	Current Anti-Virus Software Installed?
Qualtrics	Yes	Yes	Yes	Yes	Yes

Please describe any plans for study registration with an appropriate registry (e.g., clinicaltrials.gov, socialscienceregistry.org, osf.io, etc.).

MER will register this descriptive study with clinicaltrials.gov.

Goodwill of Central Texas: Fatherhood Works Healthy Marriage and Responsible Fatherhood Program Evaluation

Statistical Analysis Plan

Clinicaltrials.gov ID: NCT05292963

1. Data Analysis

Briefly describe the planned approach for data analysis. If an impact analysis is proposed, name the key dependent and independent variables, and describe any methods to minimize Type I error (i.e., finding positive impacts by chance) such as limiting the number of impacts to be analyzed and/or multiple comparison correction. Describe proposed approach(es) for addressing missing data.

Overview:

The primary analysis for this descriptive study is to assess changes in the primary and secondary outcomes presented in Table 1.1 1 year after enrollment in the Fatherhood Works Program primary services. Changes in attitudes and behaviors are assessed by comparing participant responses on the nFORM Community Fathers Entrance Survey to participant responses on the OLLE 1-year follow-up survey.

Identify study sample

The study sample includes participants who: 1) gave recorded informed consent to be part of the study, and 2) took the nFORM Community Fathers Entrance Survey, the post survey (for the parenting attitude measure), and OLLE 1-year follow-up survey (for behavioral measures and employment attitude measure). The CONSORT diagram in Appendix B shows exclusion criteria and the anticipated size of the overall study sample. The analytic sample for particular outcome measures will vary based on missing data.

Defining Analysis Measures

For each outcome construct, we have identified the relevant measures from nFORM and the OLLE Survey that are theoretically aligned with that construct. We will generate a correlation matrix between items in a given construct to ensure that theoretically related items are also empirically related in our data set. Items that are not strongly correlated with other items in a construct will be removed as necessary. Factor analysis will be used to ensure that all construct items hang together (using an alpha of 0.7 or higher as the threshold).-

----------------------	------------------------	--	---	---------	---

Handling missing data

Outcomes

When creating the composite measures for co-parenting and parenting relationships, we will create a composite score by taking the average of multiple individual items. For these measures, our current plan is to use 20% as a threshold for allowable missing items, based on guidance from evaluation technical assistance resources. This plan is contingent on the final distribution of missing data in our data set. We will not be imputing truly missing values for outcomes. To create a construct score, the average will divide by the number of non-missing values in the construct.

Participants who have not seen their child within the past month will have their parenting behavior responses set to “Never” (1) and will be included in the analytic sample for that outcome.

For outcomes that use single survey items, participants who do not respond to the item on either the pre-survey or follow-up survey will be excluded from the analytic sample for that outcome.

Missing data for the implementation outcomes could happen as a result of programmatic data entry issues. For the sake of this evaluation, we assume that any primary or support services received by a participant are being accurately logged into nFORM, so a lack of documented attendance, service contacts, referrals, etc. is indicative of lack of services (i.e., a participant not receiving the program components as intended).

Assessing non-response bias

We will conduct response rate analysis for each primary outcome of interest to assess non-response bias and adjust for threats to internal validity. Using data from the Applicant

Characteristics Survey, we will look at demographics (race, ethnicity, age, education level) and primary reason for joining the program among participants who fall into each of the following categories: 1) non-respondents who answered no surveys after the ACS, 2) respondents who completed the pre-survey only, 3) respondents who completed the follow-up survey only, and 4) respondents who completed both a pre- and follow-up survey (complete case).

Analytic approach

The main goal of this descriptive study is to assess pre-post change scores in the attitudinal outcomes listed above among program participants before (pre) and immediately following program completion, and in the behavioral outcomes listed above among program participants before and 1 year after enrolling in primary workshops. We will use paired sample t-tests to assess the magnitude and significance of changes among program participants in the analytic sample for each outcome. We will adjust our p-values for multiple hypothesis testing and report the adjusted p-values in the appendix of the final report.

For the implementation analysis, program fidelity will be descriptively reported by the percentage of enrolled participants who receive: 1) any primary workshops, 2) employment supports, 3) substantive service contacts, 4) referrals. The program aims to provide all participants each of these four program components, so the percentage of participants who receive each of these will be compared to the 100% benchmark. Number of substantive service contacts per participant will also be compared to the benchmark of 8 SSCs set by OFA for FIRE grantees.

Dosage will be measured by percent of target primary workshops participants attend on average (using 90% as a benchmark), and categories of attendance (initial, halfway, 90%, 100%) will be reported and compared to targets established by the program and reported on page 3 above. Exploratory analysis will examine how dosage varies by workshop characteristics (e.g., virtual vs in-person) and participant characteristics (e.g., age, employment status, relationship status).

2. Data Archiving and Transfer

Briefly describe the planned approach data arching and transfer by addressing questions below.

What procedures and parameters are established for all aspects of data/information collection necessary to support archiving data collected as part of the evaluation?

Examples include informed consent, data maintenance, de-identifying data procedures.

All program data, including consent forms, service data, and surveys will be maintained securely during the project period. Once the evaluation / research period is over and analysis of the data and reporting is complete, MER will de-identify the data and make them available for sharing with other researchers or on federal data sites that are appropriate and exist at that time. To facilitate this, MER will develop and implement a Data Archiving plan for this project (as it does for all such major evaluation efforts). MER's Data Archiving plan / process includes the following steps:

1. Inventorying and determining which data must be archived, and which data will not be archived or shared (such as personally identifiable information of participants)
2. Ensuring that all required data elements are maintained in a way that is compliant with OFA and OPRE guidance and regulations and best practices. This includes the creation of supporting documentation such as a code book which makes the data useable by future researchers.
3. Develop an all-inclusive archive policy for the specific data needs, which ensures that archiving is achievable and manageable, which will include the specifics on the duration of data storage (5 years), benchmarks for archiving data, the variety of media to be used for storage – both Dropbox long term storage and physical storage on secured flash drives, and rules for who will have access to the data, controlled by Dropbox controls and physical storage in a locked and fireproof storage facility.
4. Proactive protection of the data archive's integrity – by selection of the Dropbox Enterprise company to warehouse the data – using the protections described above, including the active scanning of stored data. Dropbox also includes search and discovery function, automated back-up, and total encryption.

Describe how the collection methods for all types of proposed data collection will support the archiving and transfer of each type.

Because the data collected will be combined from a secure data-based system into a tab delimited data sheet that can be exported into a variety of formats including Excel, these systems support the data

	archiving function and facilitate the sharing of data when appropriate.

How will consent form language represent plans to store data for sharing and/or transferring to other researchers?
	
The MER consent forms and processes clearly explain the use and long-term storage of data and the protection of personal and identifiable information to participants (and the de-identification of data kept long term).

Describe methods of data storage that will support archiving and/or transferring data.
	
MER's Data storage plan includes both physical and SAS (software as service) processes for long-term storage and transfer. As the data set is being built, Qualtrics and Dropbox will be the primary and redundant systems for data storage. Once all the data has been collected and the data set has been securely and completely de-identified, all data will be removed from Qualtrics, and a long-term storage file with limited access will be maintained on Dropbox. In addition, physical download of the data will be made using multiple formats and copies (flash drive and CD or other media available at the time), and these data will be stored securely in two locked locations – a bank vault and MER headquarters protected in a safe behind multiple locks and limited access.
 
When transfer is appropriate, either a secure internet-based file transfer can be used, or a delivery of a physically stored data set can be accomplished.

Explain how data and analyses file construction and documentation will support data archiving and/or transferring.
	
As part of the data analysis and clean up, a codebook will be constructed that describes the data fields and how they were collected or constructed. Supporting documentation will be stored with the data sets for easy transfer when appropriate.

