8.2. METHODS TO PROMOTE SUFFICIENT PROGRAM PARTICIPATION

Please describe methods to promote sufficient program participation in the table below.

What methods will you use to ensure sufficient sample is recruited, enrolls, and participates in the program?	GCT and their community partners will recruit program participants, and GCT will provide incentives for workshop completion and successful program referrals. GCT has implemented organizational strategies to increase program enrollment, including prioritizing referrals to Fatherhood Works for all eligible walk-in clients. GCT also meets quarterly with its community partners to talk about progress toward meeting referral targets. The CQI process will address issues regarding program recruitment, enrollment, and completion to ensure targets are met.
--	--

Who will be responsible for recruiting the evaluation sample?	The evaluation sample will not differ from the program population, in that all participants will be invited to participate in the evaluation. Enrollment into the evaluation will be conducted by the Data Manager who will conduct the informed consent process and proctor the baseline data collection efforts.
Please describe any incentives to be offered for program participation and/or completion and/or data collection and/or participation in the evaluation.	Program Participation – GCT will provide a series of incentives for workshop completion, employment retention, and successful referrals to the program, up to \$200. Evaluation Participation – The program participation incentive for reaching 100% of primary workshop hours includes exit survey completion. No incentive will be given for entrance survey completion. A \$50 Giftogram gift card will be given to participants who complete the 1-year follow-up survey.

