9.3. METHODS OF DATA COLLECTION

If the evaluation will collect multiple waves of data, describe the timing of these waves below. When describing follow-up periods, specify whether the follow-up period will be post-baseline, post-random assignment, or post-program completion.

Wave of Data Collection	Timing of Data Collection
-------------------------	---------------------------

(e.g., baseline, short-term follow-up, long-term follow-up)	
Baseline	Collected immediately following informed consent and study enrollment – during orientation session or first workshop
Post-test	Collected after the completion of the primary services programming – during the last workshop session or exit session – approximately 7 to 13 weeks after enrollment depending on delivery schedule
1 year follow-up (post-baseline)	Collected approximately one year after study enrollment/baseline

For each measure, describe how data will be collected detailing which data collection measures will be collected by which persons, and at what point in the programming or at what follow-up point.

Survey	Timing of Data Collection (baseline, wave of data collection)	Method of Data Collection	Who Is Responsible for Data Collection?	Will Methods or Collection Procedures Differ by Study Group?	Will data access require data sharing agreement?
On-Line Local Evaluation (OLLE) and nFORM Baseline Surveys	Baseline	Participant self-enters survey using online data collection platform	Data Manager will proctor data collection and assist participants as necessary	No	N/A
OLLE and nFORM Post-Test Surveys	Post-Test (approx. 7 to 13 weeks after enrollment)	Participant self-enters survey using online data collection platform	Data Manager will proctor data collection and assist participants as necessary	No	N/A

OLLE 1 Year Follow-up Survey	1 year after enrollment / baseline	Participant self-enters survey using online data collection platform and link – or – Phone interview data collection with evaluation staff	MER Research Staff/ participant tracking team	No	N/A
------------------------------	------------------------------------	--	---	----	-----

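### The SAP names data-entry gaps as a source of missing implementation data but scores every unlogged service as not received, so dosage and service-contact figures would be understated to the extent that logging is incomplete

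*SAP*

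**What the plan says.** The last paragraph on outcomes under Handling missing data (SAP section 1) begins: "Missing data for the implementation outcomes could happen as a result of programmatic data entry issues". The next sentence sets that possibility aside: "we assume that any primary or support services received by a participant are being accurately logged into nFORM". From this the SAP concludes that "a lack of documented attendance, service contacts, referrals, etc. is indicative of lack of services".

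The Analytic approach part of the same section then compares the resulting figures with fixed benchmarks:

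- **Fidelity.** For four components (any primary workshop, employment supports, substantive service contacts, referrals), "the percentage of participants who receive each of these will be compared to the 100% benchmark".
- **Contacts.** "Number of substantive service contacts per participant will also be compared to the benchmark of 8 SSCs set by OFA for FIRE grantees".
- **Dosage.** The average share of target workshops attended is set against 90%. Attendance categories, and an exploratory comparison of dosage by workshop format and participant characteristics, use the same data.

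Protocol section 11.1 says that nFORM entries are made by participants and program staff. Protocol section 6 describes a bi-weekly CQI meeting that looks at nFORM and local survey data for implementation or data problems. Neither document describes a check of nFORM service entries against another record, an estimate of the unlogged rate, or a sensitivity analysis for it.

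**The concern.** The paragraph names a cause of missing data and then sets its frequency to zero. For outcomes, the same section declines to impute truly missing values. For implementation data, a blank is in effect imputed as zero.

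The resulting error has one direction. An omitted entry can reduce attendance, a contact count or a receipt indicator, but it cannot raise any of them. Research questions I1 and I2 (protocol section 1.1) ask how much of the curriculum and other workshops was offered and received, and the planned answer is a comparison with benchmarks. A shortfall in recording would look the same as a shortfall in delivery. Goal 3 of the logic model (protocol, Evaluation Plan section 3) has the CQI team develop performance interventions where outputs fall short, so the distinction has practical consequences. If logging completeness also differs between virtual and in-person workshops, the exploratory dosage comparison would be distorted too.

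**Working it through.** **Inputs.** From the SAP: benchmarks of 90% (mean dosage), 100% (receipt of each component) and 8 (service contacts). The plan states no unlogged rate and computes no figure here, so there is nothing to reproduce. The unlogged share u is my assumption, shown at 1%, 5% and 10%. The true values of 95% and 8 are illustrative.

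**Step 1: means.** If a share u of the service received is unlogged, the reported mean is the true mean × (1 − u).

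| | u = 1% | u = 5% | u = 10% |
|---|---|---|---|
| True dosage 95% | 94.05% | 90.25% | 85.5% |
| True mean of 8 contacts | 7.92 | 7.60 | 7.20 |

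**Step 2: break-even.** The benchmark is missed through omissions alone once u exceeds 1 − benchmark/true value.

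- Dosage, true 95%: 1 − 90/95 = 5.3%.
- Dosage, true 100%: 1 − 90/100 = 10%.
- Contacts, true mean 9: 1 − 8/9 = 11.1%.
- Contacts, true mean exactly 8: any u above zero.

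**Step 3: individual counts.** If omissions are independent, a father with exactly 8 contacts keeps all 8 on record with probability (1 − u)^8. This is 0.923 at 1%, 0.663 at 5% and 0.430 at 10%.

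**Step 4: receipt of any service in a component.** A father with k loggable events is scored as unserved only if all k are omitted. If true receipt is 100% and omissions are independent, the reported share is 1 − u^k.

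| Events per father | u = 1% | u = 5% | u = 10% |
|---|---|---|---|
| 1 | 99% | 95% | 90% |
| 2 | 99.99% | 99.75% | 99% |
| 8 | about 100% | about 100% | about 100% |

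Means therefore fall in proportion to u, while receipt percentages are sensitive mainly where a component generates one or two entries per father.

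**Step 5: what other records can show.** Protocol section 9.3 says of the post-test: "Collected after the completion of the primary services programming". It may be taken in the last workshop session or in an exit session, with the evaluator's Data Manager proctoring. A post-test alongside blank attendance is thus a conflict worth resolving, but not proof of any particular dose. Protocol section 8.2 adds: "The program participation incentive for reaching 100% of primary workshop hours includes exit survey completion". It does not say which record triggers payment. If that record is the attendance log, a match against payments is circular. Neither source bears on contacts, referrals or employment supports.

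**The case against.** The strongest reply is that this is an openly stated working assumption about an administrative log. The protocol defines the implementation metrics as drawn from nFORM (section 3, Evaluation Enrollment), so reporting what nFORM holds follows the plan. The CQI team reviews those data every two weeks, and a Data Manager employed by the evaluator is embedded with the grantee. The fidelity percentages are descriptive, the 100% figure is an aim with no pass/fail rule attached, and one genuine non-attender would break it anyway.

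Much of this stands. The CQI review is a real partial safeguard, although it is not described as reconciling entries or estimating how many are missing. Disclosure makes the assumption visible but does not tell a reader how far the benchmark comparisons depend on it.

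Three stronger readings are tempting and are not supported:

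- **That the figures are biased downward as a matter of fact.** The SAP says only that gaps could occur. With complete logging there is no bias, and no rate is given.
- **That the study already holds proof of attendance for fathers with blank entries.** A post-test may come from an exit session, and even one taken in the last workshop shows a single session. The trigger for the incentive, and whether the evaluator holds payment records, are not stated.
- **That all the benchmarks are equally exposed.** Receipt percentages barely move when a father has several loggable events, and at u = 5% the illustrative 95% dosage still clears 90%.

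**Conclusion.** The point holds in conditional form. The SAP recognises a source of missing implementation data and handles it with a rule whose error runs one way, with neither a check nor a sensitivity analysis. To the extent that services go unlogged, mean dosage and contact counts would be understated in proportion. Receipt percentages would be affected chiefly for components with one or two entries per father.

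The numbers above illustrate sensitivity and do not estimate the actual bias. The proportional results need only that u is the share of service left unlogged, with equal workshop targets across fathers for dosage. Steps 3 and 4 also need independent omissions.

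The effect is confined to the implementation analyses, mainly I1 and I2, and the exploratory dosage comparisons. The paired pre-post tests for R1 to R4 do not use these data. This merits a change to the SAP but does not threaten the outcome conclusions.

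**What to change.** Amend Handling missing data in the SAP as follows.

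1. **Link and flag.** Before analysis, link post-test records to attendance by nFORM ID, which protocol section 11.2 lists for both databases. Flag fathers who have a post-test but blank or implausibly low attendance, with the threshold for the latter fixed in advance. Use incentive records only if they are held and are not derived from the attendance log.
2. **Resolve.** Route the flags through the embedded Data Manager and report how many were found and how many were corrected.
3. **Workshop receipt and dosage.** Report each figure with unresolved conflicts counted as not received (lower bound) and as received (upper bound), and compare both with the benchmark. Keep fathers who simply have no entry in the denominator. Excluding them would push receipt towards 100% by construction and remove genuine non-attenders. These bounds cover flagged conflicts only; omissions for fathers without a post-test remain undetected, and the report should say so.
4. **Contacts, referrals and employment supports.** Post-tests cannot verify these. Keep the nFORM count as the main figure, label it as logged services and hence a lower bound, and show the benchmark comparison over a range of assumed unlogged rates, for example 1% to 10%.

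The cost is SAP wording, a small amount of extra merging and some Data Manager time. The downside is that some percentages are reported as a range.
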